Appendix C

Scenario 1

Case Title: Status epilepticus in an 8-year-old child

Author: [name]

Date Last Updated: 2022-11-30

Reason for Development: Simulation research scenario

Target Population: 2nd year medical students

Target Duration: 10 minute simulation

Learning Objectives:
1. ABC approach in a sick child
2. Initiation of seizure management and review of Trekk Algorithm
3. Initiation of basic seizure investigations

Core Competencies Checklist:

Medical Expert: Professional: Communicator: Collaborator: Leader: Health Advocate: Scholar:

Crisis Resource Management Skills:

Know Environment: Anticipate & Plan: Call for help early: Distribute workload: Exercise leadership & Followership:

Mobilize all available resources: Use all information: Re-evaluate case: Prevent & Manage Fixation errors: Use good teamwork:

Communicate effectively: Allocate attention: Set priorities dynamically

Scenario Setup:

Clinical Setting: ED Resus Room: Sim Lab: Other: Ward

System: Low fi infant: Low-fi Child: High-Fi Infant: High-fi Child:

Equipment Needs:

- Bed
- Medication Cart
- IV Pump + Pole
- Defibrillator/Pacer/ECG Leads
- O₂ delivery (NP, NRB mask, BVM)
- Airway cart (Laryngoscope, ETT, etc)
- IV Catheters
- Vitals: chest leads, pulse ox, Bp cuff
- PPE
- IO Setup
- Chest tube set up
- Three-way stopcock
- Foley Catheter

Adjuncts Needed:

- ECG:
- Imaging:
- Bloodwork: Appendix A
- Videos/Photos:
- Guidelines: Appendix B
- Flowsheets:

Age: 8 yrs

Sex: Male

Wt: 30kg

Case Summary (For Facilitator):

8-year-old male presenting to the ED who has been having seizure for the past 10 minutes. His seizures will resolve following the administration of a second line anti-epileptic. The scenario is complicated by inability to obtain IV access for the first dose and worsening airway protection and desaturation as the case progresses. IV access can be obtained after an initial intranasal dose of midazolam is given.

Case Intro/Clinical Vignette (Read out loud to participants):

The paramedics are about to arrive with Rahul an 8-year-old male who is unresponsive and has been having tonic-clonic movements of his limbs for the past 10 minutes.

Additional Hx (if asked):

HPI: previous well

PMH: Nil

Meds: Nil

Algs: Nil

Stage 1:

Patient Condition	Simulator Parameters	Effective Management	Consequences of ineffective management	Notes:

General: Unresponsive, no work of breathing, normal colour
 
Airway: No stridor, neck flexed,
 
Breathing: No WOB, normal chest rise
 
Circulation: Normal pulses, cap refill <3, warm extremities
 
Disability: Unresponsive, Pupils dilated, reactive
 
P/E: Cardio: Unremarkable Resp: Unremarkable Abdo: unremarkable Neuro: Pupils dilated, no reflexes, stiff tone, repeated flexion of arms, head deviation to one side
	
HR: 122 RR: 10 SaO₂: 90% BP: 110/75 Temp: 37.7C
	
A:
 
 • Attempt better positioning • Jaw thrust • Suction • Oral Airway 
B:
 
 • O₂ by non-rebreather or facemask 
C:
 
 • Attempt IV access • Cycle BP's 
Monitors:
 
 • Chest leads, sat monitor, BP Cuff 
Investigations:
 
 • POC Glucose (4.0) • Blood work 		
 • IV access is unsuccessful

		Medications: 
 Intranasal Midaz or Diazepam PR 		
--	--	---	--	--

Stage 2:

Patient Condition	Simulator Parameters	Effective Management	Consequences of ineffective management	Notes:

General: 5 minutes have passed, and patient is continuing to seize
 
Airway: No intervention: Mild stridor, poor position Intervention: supported effectively
 
Breathing: If no jaw thrust mild work of breathing, otherwise unremarkable
 
Circulation: Normal pulses, normal cap refill
 
Disability: Unresponsive
 
P/E: Unchanged
	
HR: 126 RR: 12 SaO₂: 84% if no intervention 95 if O₂ and airway management BP: 112/80 Temp: 37.8
	
A:
 
 Airway management above if not completed 
B:
 
 Nil 
C:
 
 Obtain IV access 
Medication:
 
 Lorazepam IV Keppra IV or other second line agent 	
Need to get to second line agent to abort seizure
	

Expected / Critical Actions	Unacceptable Actions:

 Attempted IV access and repeat attempt later 	
 No airway management when patient is stridulous

- Transition to Non-IV medication when access unavailable
- Call for support (Neuro) if seizure continues

Medical Expert Points to bring up for discussion:

- Intranasal midazolam vs IV Lorazepam and effectiveness
- Importance of airway management
- Work-up for unknown seizure (Glucose, lytes)

Lab	Result	Normal Range
CBC		
WBC	7 x 10 ⁹	4-12x10 ⁹
Hgb	130	130 – 160
Plt	320	150 – 450
Glucose	5.7	
Electrolytes & Extended electrolytes:		
Sodium (Na ⁺)	140	135 – 145
Potassium (K ⁺)	4.2	3.5 – 5.5
Chloride (Cl ⁻)	103	102 – 112
Ionized Calcium (iCa)	1.18	1.15 – 1.3
Phosphate (PO ₄ ⁻²)	1.5	1.16 – 1.81
Magnesium (Mg ²⁺)	0.8	0.66 – 0.91

Scenario 2

Case Title: Status epilepticus in a 1-year-old child

Author: [name]

Date Last Updated: 2022-11-30

Reason for Development: Simulation research scenario

Target Population: 2nd year medical students

Target Duration: 10 minute simulation

Learning Objectives:
1. ABC approach in a sick child
2. Initiation of seizure management and review of Trekk Algorithm
3. Initiation of basic seizure investigations

Core Competencies Checklist:

Medical Expert: Professional: Communicator: Collaborator: Leader: Health Advocate: Scholar:

Crisis Resource Management Skills:

Know Environment: Anticipate & Plan: Call for help early: Distribute workload: Exercise leadership & Followership:

Mobilize all available resources: Use all information: Re-evaluate case: Prevent & Manage Fixation errors: Use good teamwork:

Communicate effectively: Allocate attention: Set priorities dynamically

Scenario Setup:

Clinical Setting: ED Resus Room: Sim Lab: Other: Ward

System: Low fi infant: Low-fi Child: High-Fi Infant: High-fi Child:

Equipment Needs:

- Bed
- Medication Cart
- IV Pump + Pole
- Defibrillator/Pacer/ECG Leads
- O₂ delivery (NP, NRB mask, BVM)
- Airway cart (Laryngoscope, ETT, etc)
- IV Catheters
- Vitals: chest leads, pulse ox, Bp cuff
- PPE
- IO Setup
- Chest tube set up
- Three-way stopcock
- Foley Catheter

Adjuncts Needed:

- ECG:
- Imaging:
- Bloodwork: Appendix A
- Videos/Photos:
- Guidelines: Appendix B
- Flowsheets:

Age: 1 yr

Sex: Female

Wt: 10kg

Case Summary (For Facilitator):

1-year-old girl presenting on the ward who has been having seizure for the past 5 minutes. Her seizures will resolve following the administration of a second line anti-epileptic. The scenario is complicated by inability to obtain IV access for the first dose and worsening airway protection and desaturation as the case progresses. IV access can be obtained after an initial intranasal dose of midazolam is given.

Case Intro/Clinical Vignette (Read out loud to participants):

The nurse calls you about with Zoe a 1-year-old girl who is unresponsive and has been having tonic-clonic movements of her limbs for the past 5 minutes. She was admitted for gastroenteritis and pulled her IV out earlier today.

Additional Hx (if asked):

HPI: previous well

PMH: Nil

Meds: Nil

Algs: Nil

Patient Condition	Simulator Parameters	Effective Management	Consequences of ineffective management	Notes:

General: Unresponsive, no work of breathing, normal colour
 
Airway: No stridor, neck flexed,
 
Breathing: No WOB, normal chest rise
 
Circulation: Normal pulses, cap refill <3, warm extremities
 
Disability: Unresponsive, Pupils dilated, reactive
 
P/E: Cardio: Unremarkable Resp: Unremarkable Abdo: unremarkable Neuro: Pupils dilated but reactive,, no reflexes, stiff tone, repeated flexion of arms, head deviation to one side
	
HR: 170 RR: 14 SaO₂: 90% BP: 95/55 Temp: 37.6C
	
A:
 
 • Attempt better positioning • Jaw thrust • Suction • Oral Airway 
B:
 
 • O₂ by non-rebreather or facemask 
C:
 
 • Attempt IV access • Cycle BP's 
Monitors:
 
 • Chest leads, sat monitor, BP Cuff 
Investigations:
 
 • POC Glucose (2.0) • Blood work 
Medications:
 
 • Intranasal Midaz or Diazepam PR 
Call for help
		
 • IV access is unsuccessful

Stage 2:

Patient Condition	Simulator Parameters	Effective Management	Consequences of ineffective management	Notes:

General: 5 minutes have passed, and patient is continuing to seize
 
Airway: No intervention: Mild stridor, poor position Intervention: supported effectively
 
Breathing: If no jaw thrust mild work of breathing, otherwise unremarkable
 
Circulation: Normal pulses, normal cap refill
 
Disability: Unresponsive
 
P/E: Unchanged
	
HR: 126 RR: 12 SaO₂: 84% if no intervention 95 if O₂ and airway management BP: 112/80 Temp: 37.8
	
A:
 
 Airway management above if not completed 
B:
 
 Nil 
C:
 
 Obtain IV access 
D:
 
 IV D10W 
Medication:
 
 Lorazepam IV Keppra IV or other second line agent 	
 Need to get to second line agent to abort seizure Should correct glucose to stop seizure. 	

Expected / Critical Actions	Unacceptable Actions:

 Attempted IV access and repeat attempt later Transition to Non-IV medication when access unavailable Call for support (Neuro/Staff) if seizure continues 	
 No airway management when patient is stridulous

Medical Expert Points to bring up for discussion:

- Intranasal midazolam vs IV Lorazepam and effectiveness
- Importance of airway management
- Work-up for unknown seizure (Glucose, lytes)

Lab	Result	Normal Range
CBC		
WBC	8 x 10 ⁹	4-12x10 ⁹
Hgb	145	130 – 160
Plt	270	150 – 450
Glucose	4.2	
Electrolytes & Extended electrolytes:		
Sodium (Na ⁺)	144	135 – 145
Potassium (K ⁺)	4.5	3.5 – 5.5
Chloride (Cl ⁻)	103	102 – 112
Ionized Calcium (iCa)	1.2	1.15 – 1.3
Phosphate (PO ₄ ⁻²)	1.4	1.16 – 1.81
Magnesium (Mg ²⁺)	0.8	0.66 – 0.91

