B Respiratory Failure	
 Apnea/poor effort Increased work of breathing Air entry Added Sounds: Wheeze/Crackles SpO₂, RR, End-tidal CO₂ 	
 Bag-mask ventilation Positive Pressure (HFNC, CPAP, BiPAP) Prepare for intubation if needed Medications for respiratory distress (Asthma) Pneumothorax – Needle decompression, Chest tube

Respiratory issues are typically secondary to airway compromise in seizures

Primary Survey – C - Circulation

Recognize	Assess for	Manage
C Shock	
 Tachycardia, Bradycardia Cap Refill (Fast/Slow) Pulses Hypotension (late sign) Hepatomegaly Check pelvis stability 	
 Think about access - IV, IO, Central Line Isotonic Fluid Bolus – 10-20ml/kg at a time Consider epinephrine or norepinephrine

Seizing patients should be tachycardic and normotensive or slightly hypertensive.
Hypotension and/or bradycardia is very concerning.

Primary Survey – D - Disability

Recognize	Assess for	Manage
D Severe Head Injury Raised ICP Seizure	
 GCS less than or equal to 8 Respond only to pain/unresponsive Cushing's Triad (Bradycardia, Hypertension, Irregular resp) 	
 Head of bed elevation, head midline Intubation/Sedation 3% hypertonic saline – 5ml/kg Hyperventilation if herniation (Blown Pupil) Neurosurgery consult

AVPU: Alert → Verbal → Pain → Unresponsive

Primary Survey – E - Exposure

E	Recognize	Assess for	Manage
	
 Rashes Signs of Trauma 	
 Purpura Bruising Abrasions 	
 Maintain Normothermia

Not always a core component of seizure assessment but may give clues to etiology

Estimating your patients weight

Practical Estimation based on Age:

- Infants <12mo: (age in months + 9)/2
- Children 1-5: (age + 5) x 2
- Children 5-14: Age x 4

When poll is active, respond at [pollev.com/[name]](https://poll.ev.com/[name])

You don't have an IV how can you give a benzodiazepine to stop the seizure?

IV access only	Oral
	Sublingual
	Intranasal
	Rectal
	Intraosseous
	Intramuscular

Powered by [Poll Everywhere](https://poll.ev.com)

First line Treatment

Phase 1 5-15 min

Prehospital	First Line Agents

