
 Give Midazolam IM/intranasal (NI see dosing table). Check blood glucose: If blood glucose <3.3 mmol/L (<60 mg/dL): Treat with D2BW 2 mL/kg/dose IV (MAX 100 mL/dose) OR D10W 5 mL/kg/dose IV (MAX 200 mL/dose). If still seizing after 5 minutes, give Midazolam second dose. MAX cumulative dose 10 mg in prehospital setting. 	No IV/IO Midazolam IM or IN: <13 kg: 0.2 mg/kg/dose; 13-40 kg: 5 mg/dose; >40 kg: 10 mg/dose; MAX 10 mg/dose
Emergency Department (ED) 
 Give benzodiazepine if two doses not already given prior to ED arrival (see dosing table). Check blood glucose if not already done. Treat hypoglycemia as above. Reassess blood glucose in 5 minutes. Give second benzodiazepine dose for ongoing seizures 5 minutes after first dose. When IV/IO access available, switch to IV/IO route. CAUTION: Do not give more than 2 doses of benzodiazepines.	IV/IO Lorazepam IV/IO: 0.1 mg/kg/dose; MAX 4 mg/dose Midazolam IV/IO: 0.1 mg/kg/dose; MAX 10 mg/dose

Reassess ABCs, monitor for respiratory depression. If still seizing give one of these second-line agents.

Respond at [pollev.com/[name]](https://poll.ev.com/[name])

6yr old patient who was seizing on the ward for 30 minutes and have received 3 doses of midazolam to try to abort their seizure. They now have very minimal respiratory effort. What is cause?

[figure not shown]
Prolonged Seizure
Poor positioning/Obstruction
To many benzodiazepines
Sepsis

Powered by [Poll Everywhere](https://poll.ev.com)

Benzodiazepines – First Line

Drug and route	Dose	Maximum
Midazolam	0.1 mg/kg	5 mg
• IV, IO		
• IM	0.2 mg/kg	10 mg
• Buccal	0.5 mg/kg	10 mg
• Intranasal	0.2 mg/kg	10 mg (5 mg per nostril)
Lorazepam	0.1 mg/kg	4 mg
• IV, IO, Buccal		
Diazepam	0.3 mg/kg	5 mg (<5 years); 10 mg (≥5 years)
• IV, IO		
• PR	0.5 mg/kg	20 mg

MAX DOSES: TWO

Side Effects of too many Benzodiazepines

- Respiratory depression
- Hypotension
- Sedation

Second Line Treatment

Repeat one different second line medication 5 mins after infusion

Phase 2
15-20 min

Drug	Dose	Age	Comments/Cautions
Levetiracetam	40 mg/kg/dose IV/IO (MAX 3000 mg/dose) infuse over 5 minutes	Any age	↓ side effects/drug interactions, low risk of psychosis

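### Appendix C, Scenario 2: the 1-year-old's Stage 2 simulator settings duplicate the 8-year-old's and do not follow from her own Stage 1, and her two glucose values are not reconciled

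*Combined protocol and SAP*

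**What the plan says.** Appendix C contains two status epilepticus scripts: Scenario 1, an 8-year-old of 30 kg, and Scenario 2, a 1-year-old of 10 kg. Each has two stages with a column of simulator settings.

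- Scenario 1, Stage 1: "HR: 122 RR: 10 SaO₂: 90% BP: 110/75 Temp: 37.7C".
- Scenario 2, Stage 1: "HR: 170 RR: 14 SaO₂: 90% BP: 95/55 Temp: 37.6C".
- Stage 2, in both scenarios: "HR: 126 RR: 12 SaO₂: 84% if no intervention 95 if O₂ and airway management BP: 112/80 Temp: 37.8".

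In both scripts Stage 2 opens five minutes on, with the child still seizing. Neither Stage 2 table gives an event that would explain a change in heart rate or blood pressure.

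On glucose, Stage 1 of Scenario 1 gives "POC Glucose (4.0" and Stage 1 of Scenario 2 gives "POC Glucose (2.0". The laboratory sheets that follow show 5.7 and 4.2 respectively, with no unit, reference range or draw time for glucose. The lecture in Appendix B sets the treatment threshold with the words "If blood glucose <3.3 mmol/L (<60 mg/dL".

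On what ends the seizure, the facilitator summary of Scenario 2 names a second-line drug. Its Stage 2 table says both that a second-line drug is needed and that correcting the glucose should stop the seizure.

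Section 3.1 lists the primary outcome as the global rating plus five time-to metrics: glucose check, IV access, chemistry panel order, first-line drug and second-line drug. Section 5.4 describes the 3-month evaluation but does not say which scenario is run.

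**The concern.** A scenario script is part of the measuring instrument. Raters score what the student does in response to what the mannequin and the laboratory sheet show. If the child's observations change sharply for no scripted reason, or two results for the same analyte disagree across a treatment threshold, students and facilitators have to improvise. That variation has nothing to do with retention.

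Section 5.3 says the lecture's objectives were matched to the outcome measures, so agreement between lecture and script matters here. The lecture states "Seizing patients should be tachycardic and normotensive or slightly hypertensive" and lists "Cushing's Triad (Bradycardia, Hypertension, Irregular resp" among the signs to assess for under disability. A heart rate that drops while pressure climbs moves in that general direction, although the script intends no such event. A student who orders the chemistry panel, itself a scored step, may be given a glucose that undercuts the bedside result.

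The two accounts of what ends the seizure bear directly on a listed metric. One facilitator could let the seizure stop after dextrose and another could hold out for the second-line drug, so time to second-line drug would depend on how the script was read.

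**Working it through.** The plan gives no statistical figure on this point to reproduce, and the sample size in section 6.1 does not enter. The check is a comparison of the script's own entries.

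**Step 1. Are the Stage 2 cells the same?** A character-by-character comparison of the two cells finds no difference. All five parameters (heart rate, respiratory rate, saturation, blood pressure, temperature) match, although the Stage 1 sets differ.

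**Step 2. Does each Stage 2 follow from its own Stage 1?** Change = Stage 2 minus Stage 1; percentage = change divided by Stage 1.

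| Parameter | Scenario 1 | Change | Scenario 2 | Change |
|---|---|---|---|---|
| Heart rate | 122 to 126 | +4 (+3.3%) | 170 to 126 | −44 (−25.9%) |
| Respiratory rate | 10 to 12 | +2 | 14 to 12 | −2 |
| Systolic pressure | 110 to 112 | +2 (+1.8%) | 95 to 112 | +17 (+17.9%) |
| Diastolic pressure | 75 to 80 | +5 (+6.7%) | 55 to 80 | +25 (+45.5%) |
| Temperature | 37.7 to 37.8 | +0.1 | 37.6 to 37.8 | +0.2 |

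The Stage 2 values continue Scenario 1 smoothly. In Scenario 2 they reverse the direction of heart rate and respiratory rate and produce a large rise in pressure.

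**Step 3. Do the glucose values agree?** No unit is printed for the scenario values; mmol/L is assumed, to match the lecture.

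- Scenario 1: 5.7 − 4.0 = 1.7, with both values above 3.3.
- Scenario 2: 4.2 − 2.0 = 2.2, a ratio of 4.2/2.0 = 2.1. The bedside value is below 3.3 and the laboratory value above it.

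Blood work is listed in Stage 1 beside the bedside glucose, where IV access fails. Intravenous dextrose first appears in Stage 2. The laboratory value could therefore precede or follow dextrose, and nothing says which. A laboratory value above the bedside one does not itself signal correction, because Scenario 1 shows the same pattern with no dextrose in its script.

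**Step 4. Which outcomes are exposed?** In Scenario 2, glucose check, blood work, the first IV attempt and the first-line drug are Stage 1 actions. A student who performs them on script does so before the Stage 2 settings appear. The glucose metric times the check, not the value returned; the chemistry metric times the order, not the result. Time to dextrose is not an outcome. That leaves chiefly the global rating and time to second-line drug, along with IV access if the metric counts success and not the attempt.

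**The case against.** Four stronger readings are tempting, and the documents support none of them.

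- **Bias between arms.** A reader might infer that students who retained more of the lecture would be thrown off more, which would pull the better arm toward the other. Both arms receive the same lecture, and nothing suggests that the evaluation case differs by arm. The inference needs better retainers to notice the change, to be diverted by it and to be marked down for it. None of these steps is documented, and the share of students diverted is unknown.
- **A false sign of raised intracranial pressure.** The slide names bradycardia, not a fall from tachycardia. The lecture text available gives no age-specific ranges, so no section makes 126 a bradycardia or takes 112/80 beyond the slight hypertension that the lecture allows. The script describes no irregular breathing.
- **A contradiction with the unchanged examination.** Stage 2 marks the physical examination as unchanged, but vital signs sit in a separate column. Scenario 1 uses the same entry while its vital signs also move.
- **The glucose values flatly contradict each other.** The laboratory sample is untimed and could follow dextrose. What is shown is two values on opposite sides of a threshold with no label to explain them.

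It is also fair to say that the use of Scenario 2 at 3 months is an inference from the numbering. If Scenario 2 were used at the initial session instead, the inconsistency would sit in that session's ratings, since sections 3.1 and 5.2 provide for a global rating of each simulation.

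What stands after all this is the duplicated cell, the unexplained step from Stage 1, the unlabelled glucose value and the two accounts of what ends the seizure.

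**Conclusion.** The inconsistency is real and lies in the script that the simulator runs for a scored session. All five Stage 2 parameters of Scenario 2 equal those of Scenario 1, and they imply a heart-rate fall of 44 and a pressure rise of 17/25 with no scripted cause, against +4 and +2/+5 in the older child. A carried-over cell is the natural explanation but is not proven. The glucose values of 2.0 and 4.2 straddle 3.3, assuming mmol/L.

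If Scenario 2 is the 3-month case, the consequence is added noise and weaker validity, mainly for the global rating and time to second-line drug. The size of that effect cannot be computed from the documents. Bias between arms is not shown, and most of the time-to metrics are little exposed. The point is worth acting on because the correction is small and specific, not because the primary comparison has been shown to fail.

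**What to change.** Before the first 3-month evaluation, the trial's clinicians should do the following in one edit of Appendix C:

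- Reconcile the Scenario 2 Stage 2 settings with that scenario's Stage 1 values.
- Reconcile the Scenario 2 laboratory glucose with the bedside glucose, or label when the sample was drawn and what it follows.
- Reconcile the facilitator summary and the Stage 2 table on what ends the seizure.

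The clinical values and rules are theirs to choose; none is proposed here. Section 5.4 should also name the scenario used at each session. One version should then be locked for all participants.

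The cost is a few entries in one scenario, one line on its laboratory sheet, one sentence in the protocol and reprogramming one simulator stage. If any student has already been assessed on the unreconciled script, that student should be flagged in the dataset.

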3.1 Outcome Measures

The primary outcome will be the resuscitation performance retention assessed using the post-teaching the final global rating scale score (1-7 performance score) for medical management and flow during each simulation as well as the following “time-to” metrics; glucose check, IV access, chemistry panel order, first-line anti-epileptic administration³⁰, second line anti-epileptic administration. This will be adjusted for baseline score.

The secondary outcome measures for knowledge retention assessment will be the post-teaching knowledge test score assessed on a 15 Question MCQ test administered at the final assessment adjusted for the baseline score.

Comfort/Confidence will be assessed using the change in Likert scale item after each simulation and debrief.

4 Study Population

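### Scenario 2 does not say clearly whether correcting glucose ends the seizure; if facilitators let it, some students lose the trigger for second-line treatment, one of the primary time-to metrics

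*Combined protocol and SAP*

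**What the plan says.** Section 3.1 puts five time-to metrics in the primary outcome beside the global rating score. They include time to glucose check and time to "second line anti-epileptic administration". Section 6.2 analyses the time-to measures with Kaplan-Meier curves, the log-rank test and, secondarily, Cox models. It gives no censoring time and no rule for a seizure that ends before the timed drug is due.

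Appendix C, Scenario 2, has three statements about what ends the seizure:

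- Case Summary, addressed to the facilitator: "Her seizures will resolve following the administration of a second line anti-epileptic".
- Stage 2, first bullet on ineffective management: "Need to get to second line agent to abort seizure".
- Stage 2, the bullet after it: "Should correct glucose to stop seizure".

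Bedside glucose is 2.0 in Scenario 2 and 4.0 in Scenario 1. The Appendix B lecture treats values below 3.3 mmol/L during first-line treatment ("Check blood glucose if not already done. Treat hypoglycemia as above") and makes the next step conditional: "If still seizing give one of these second-line agents".

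**The concern.** The student sees the mannequin, not the script. If it stops seizing after dextrose, a student who follows the lecture has no reason to give the drug being timed. A correct action, close to another primary metric (glucose check), would then close off the second-line event. Two facilitators could run the same page differently. Two analysts could also code such a student differently: as not treated by 10 minutes, or as censored when the seizure ended. At stake are the number of second-line events and the power of that one comparison.

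**Working it through.** **1. The script, side by side.**

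| Item | Scenario 1 | Scenario 2 |
|---|---|---|
| Bedside glucose | 4.0 | 2.0 |
| Dextrose in Stage 2 | none | IV D10W, listed above the second-line agent |
| Second-line drug ends seizure | yes | yes |
| Added line on glucose and the seizure | none | yes |

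The glucose line was added for Scenario 2 only. It allows three readings: the drug alone ends the seizure, both treatments are needed, or either is enough. Only 'either' closes the second-line event.

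**2. Who could be affected.** IV access fails in Stage 1 and becomes available after intranasal midazolam. D10W is listed only in Stage 2, as an IV treatment. An affected student must check glucose, give midazolam, obtain the IV and give D10W before the second-line drug, all within 10 minutes. The facilitator must then stop the seizure. Call the share g. It is 0 if the Case Summary is followed. The documents give no other information on it.

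**3. The plan's own figure.** The total of 60 in section 6.1 reproduces with the LS-group SD: 2 × (18.59 × (1.960 + 0.842) / 13.42)² = 30.1 per arm (60 to the nearest whole number per arm, 62 rounded up). It rests on a percentage skill score, so the plan states no power for any time-to metric. I take 30 per arm from it, assuming 1:1 allocation.

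**4. Illustration.** All timings are assumptions. First dose t1 is lognormal with log-SD 0.5 and median 3.5 min (LS) or 2.5 min (SL). The second-line drug follows at t1 + 5 min, and the scenario stops at 10 min. Without glucose stops, P(event) = Φ(ln(5/m)/0.5), where m is the median:

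- LS: Φ(0.713) = 0.762
- SL: Φ(1.386) = 0.917
- Events: 30 × (0.762 + 0.917) = 50.4

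An equal stop share g in both arms leaves 50.4 × (1 − g) events. Power comes from simulated two-sided 5% log-rank tests, with students who never receive the drug censored at 10 minutes:

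| g in each arm | Events | Power to favour SL |
|---|---|---|
| 0 | 50.4 | about 67% |
| 10% | 45.3 | about 45% |
| 25% | 37.8 | about 27% |
| 50% | 25.2 | about 12% |

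Power falls faster than events because stopped students stay in the risk set to the end and pull the hazard ratio towards 1 (about 2.0 at g = 0, 1.39 at g = 50%). Censoring at the end of the seizure instead gives about 64% at g = 10% and 50% at g = 50%, if stops are spread evenly between t1 and t1 + 5.

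**5. Bias.** With equally fast arms (median 3 min in both) and equal g, the estimated hazard ratio stays near 1 and each arm is falsely favoured in about 3% of trials. With g of 5% in LS and 10% in SL, censoring at 10 minutes falsely favours LS in about 6%. Larger distortions need larger gaps between arms, and no document supplies one.

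**The case against.** The best defence is that the page already has an answer. The Case Summary speaks to the person running the mannequin and names only the second-line drug. The first Stage 2 bullet says that drug is needed, which would be false on the 'either' reading. The glucose bullet sits in a column about ineffective management and can be read as advice to the learner. This largely stands: 'either' is the reading the page supports least. It does not remove the ambiguity, because the bullet ties glucose correction to stopping the seizure and appears only where glucose was set low.

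The chain in step 2 is also demanding for second-year students, so g may be small. That stands.

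Stop times spread from t1 would include Stage 1, before D10W is listed. That weakens the figures for censoring at the end of the seizure. It does not touch the table, because censoring at 10 minutes ignores when the seizure stopped.

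A reader might infer that the script makes second-line treatment unreachable, or that the trial would favour the wrong arm. The documents support neither. The first needs every facilitator to depart from the Case Summary. The second needs a sizeable difference in g between arms, yet both arms hear the same lecture. Nor is the planned method unsuitable: log-rank and Kaplan-Meier accept censored students, and what is missing is the rule.

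**Conclusion.** The ambiguity is real and bears on one of five primary time-to metrics. Harm requires three things: Scenario 2 is the 3-month case, a facilitator stops the seizure after D10W, and some students give D10W before the second-line drug. If Scenario 2 is instead the first case, only the baseline measurement is touched. Given those conditions, the likely cost is power on this metric: from about 67% to about 45% or 27% at equal stop shares of 10% or 25%, on assumed timings and censoring at 10 minutes. With no such stops there is no loss. The global rating score and the sample size calculation are unaffected. Severity is minor to moderate.

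**What to change.** Before evaluation visits begin:

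1. In Scenario 2, Stage 2, replace the glucose bullet with: *D10W corrects the glucose; the seizure continues until a second-line agent is given.* This agrees with the Case Summary and keeps the event open to every participant.
2. In section 6.2, add: *Participants with no second-line drug by 10 minutes are censored at 10 minutes.* This sentence alone would not recover the power; the script line does that.

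The cost is one line and one sentence, with no extra visits or data. The downside is slightly less clinical realism, since the child keeps seizing after glucose is corrected. The global rating can still credit the correction.

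If evaluation visits have begun, leave the script alone so that all participants face the same case. Have the masked reviewers record from the existing video any seizure that ended after glucose and before a second-line drug, and report those counts by arm beside the second-line result. Fix the primary coding before unmasking. Calling these stops a competing event does not settle it: a cause-specific log-rank test matches censoring at the end of the seizure, while a subdistribution test with a fixed 10-minute end matches censoring at 10 minutes.
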